SLEEP QUALITY AND HUMAN AMYLOID-BETA KINETICS
NCT: NCT03077620
DATE: MARCH 3, 2020

HSC Protocol: Sleep Quality and Human Amyloid-Beta Kinetics

Background

Alzheimer's disease (AD) is a growing public health crisis with over 5 million Americans currently afflicted. With no disease-modifying or prevention treatments for AD, this number is predicted to increase to 13.5 million by 2050 (29). Even a modest reduction in AD risk in our aging population would have a tremendous impact on public health: delaying the onset of AD by 5 years would halve disease prevalence. The amyloid hypothesis supports that amyloid- β (A β) deposition in the brain is a key first-step in AD pathogenesis (30). Changes of 25-40% in A β production have been shown to completely protect or cause AD in humans (31, 32), therefore A β has become a primary target for therapies to prevent AD.

Recent evidence supports a role for sleep in the development of AD, at least in part, via an A β mechanism. There is a diurnal pattern in A β levels in both mice and humans: levels are higher in the brain interstitial fluid (ISF) of mice and in human cerebrospinal fluid (CSF) during wakefulness and lower during sleep (6, 8). Experimental evidence has also shown that A β levels are modifiable under different sleep conditions (8). My research translated these findings to humans, showing that sleep deprivation increases CSF A β 40 and A β 42 compared to participants treated with a sleep-inducing medication or those with normal sleep (control). Further, preliminary data suggests that higher sleep efficiency (total sleep time/time in bed) is associated with a reduction in A β concentration in both the sleep-induced with drug and control groups. These findings suggest the potential to prevent or delay AD by decreasing CSF A β concentrations with therapies that improve sleep efficiency.

This study proposes to directly assess CSF A β kinetics (i.e. production and clearance rates) and concentration in humans with good vs. poor sleep efficiency and their response to pharmacologic sleep induction. We hypothesize that 1) poor sleep efficiency increases CSF A β production and concentration compared to good sleep efficiency, and 2) sleep induction in individuals with poor sleep efficiency will decrease CSF A β production and concentration. Specific Aims 1 and 2 will address each hypothesis:

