45 participants will be randomized to receive a placebo, 10 mg of suvorexant, 20 mg of suvorexant during the CRU stay. Suvorexant is a dual orexin receptor antagonist that is approved by the Food and Drug Administration (FDA) for the treatment of insomnia. Suvorexant is also a drug with the same mechanism of action as was used in experiments to decrease A β with sleep in mice (8), therefore this will be a direct translation of this finding. Further, genetic manipulation of the orexin system to alter the sleep-wake cycle has been shown to drive A β pathology (51).

FDA-approved doses of suvorexant range from 5-20 mg. The drug's mechanism of action is to block orexin-A and orexin-B receptors. The orexin neuropeptide acts in the brain to promote wakefulness. Through antagonism of this system, sleep is induced. In a phase IIb randomized, double-blind, placebo-controlled study of patients with primary insomnia, suvorexant 10 mg increased sleep efficiency from 65.1% at baseline to 82.9% at night 1 and 84.4% at one month (48). Placebo-treated subjects increased sleep efficiency from 65.9% at baseline to 76.8% at night 1 and 77.8% at one month.

Participants will be allowed to sleep as they are able immediately with the lights turned off after medication dispensation (placebo or suvorexant). Nursing staff will use dim red lights (safelights) when collecting CSF and blood in the dark. The lumbar catheter ports will be placed on the outside of the gown sleeve for easy access to minimize disturbance during fluid collection. Participants will then sleep until final awakening the morning. During Day 2, all participants will be in well-lit rooms with regular monitoring for

staying awake and naps will not be permitted. On Day 2 ($t=24$), all participants will follow the same sleep routine except that there will be no infusion of labeled $^{13}\text{C}_6$ -leucine. Participants will receive the same placebo or suvorexant dose as the previous night (Figure 5). The IVs and lumbar catheters will be removed following the last CSF collection ($t=36$). Afterwards, participants will be monitored at the Clinical Research until discharge at approximately 17:00. A β kinetics will be quantified by MS.

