Statistical Analysis and Power Calculation: All participants will be screened to determine if they have good or poor sleep efficiency as described above. 15 participants with good sleep efficiency will be treated with placebo (Aim 1). 45 participants with poor sleep efficiency will be randomized to either placebo (N=15) (Aim 1) or suvorexant 10 mg (N=15) or suvorexant 20 mg (N=15) (Aim 2). Change in CNS A β 40 and A β 42 production, clearance, and concentration in placebo-treated participants with poor sleep efficiency will be compared to placebo-treated participants with good sleep efficiency (Aim 1) and individuals with poor sleep efficiency treated with suvorexant (Aim 2) using a repeated measures analysis of variance (RM ANOVA), or repeated measures analysis of covariance (RM ANOCOVA) when covariates such as age are included in the analysis (49). Correction for multiple comparisons will be performed. A main question is whether the production rate of CSF A β during the production phase differs between subjects with good or poor sleep efficiency, or treated with drug, that will be statistically tested by appropriate interactions between subjects groups and time in the RM ANOCOVA. The average concentration of CSF A β over the entire time course during the sleep period will be tested by the main effects of subjects' groups, adjusting for the possible effects of age. Other parametric mixed effects models incorporating the typical sinusoidal profile over time will also be considered in the analyses. These analyses will be implemented by PROC MIXED/SAS or SPSS (50).

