To determine the sample size, I performed an *a priori* calculation with two-tailed t-tests to detect a difference between two independent means (two groups) for the number of subjects needed to find a difference in the AUC for both A β 40 and A β 42 during the 10-hour sleep period. With the preliminary data for control (good and poor sleep efficiency) and all sleep-induced participants, the mean and standard deviation of A β 40 and A β 42 AUCs (pM*hr) during the 10-hour period from 23:00-09:00 were used for the power calculation (see Table 1: “Control – Poor Sleepers (N=4)”, “Control – Good Sleepers (N=3)”, and “Sleep-Induced (N=8)”). We will be able to detect similar pM*hr differences as from the preliminary data between all groups and all A β isoforms with 13 participants in each group (effect size d range=1.17-1.57, $\alpha = 0.05$, Power $(1-\beta) = 0.8$), therefore this study is adequately powered with 15 participants in each group.

Alternative Approaches: We chose serial CSF collection via lumbar catheterization for the experimental approach because it provides the most detailed measures of A β kinetics and concentrations. An alternative approach could be to perform $^{13}\text{C}_6$ -leucine labeling with one lumbar puncture performed after the sleep period; differences in A β kinetics could be inferred by percent labeling of A β . However, with this approach the time relative to each participant's final awakening may be variable for each participant (e.g. 08:00 vs. 09:00) and does not easily account for different sleep start times. A larger sample size may also be required with this approach. Other potential problems for this study include participant recruitment and study completion. This study is intensive for participants. However, our preliminary study is similarly intensive and we have been able to achieve participant recruitment and completion goals. Screening participants by good and poor sleep efficiency may be more difficult than anticipated because participants will initially be referred from the community-based participant registry, Volunteers for Health, based on self-report and questionnaires. These measures may not correlate with the sleep efficiency found by actigraphy. If this occurs, we will need to screen more participants than

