 - Sleep efficiency measured by actigraphy – this will be determined following enrollment and participants not meeting this criterion will be excluded from further participation in the study
 - Good sleep quality group: Sleep efficiency $\geq 85\%$ [Aim 1]
 - Poor sleep quality group: Sleep efficiency $< 85\%$ [Aims 1 and 2]
- Exclusion criteria:
 - Cognitive impairment as determined by history of MMSE < 27
 - Inability to speak or understand English
 - Any sleep disorders other than insomnia
 - No history of sleep-disordered breathing and STOP-Bang score > 3
 - History or reported symptoms suggestive of restless legs syndrome, narcolepsy or other sleep disorders
 - Sleep schedule outside the range of bedtime 20:00-midnight and waketime 04:00-09:00
 - Contraindication to lumbar catheter (anticoagulants; bleeding disorder; allergy to lidocaine or disinfectant; prior central nervous system or lower back surgery)
 - Cardiovascular disease requiring medication except for controlled hypertension (PI discretion)
 - Stroke
 - Hepatic or renal impairment
 - Pulmonary disease (PI discretion)
 - Type 1 diabetes
 - HIV or AIDS
 - Neurologic or psychiatric disorder requiring medication (PI discretion)
 - Suicidal ideations
 - Alcohol or tobacco use (PI discretion)
 - Use of sedating medications (PI discretion)
 - Inability to get out of bed independently
 - Abnormal movement of the non-dominant arm (would affect actigraphy data in unpredictable ways)
 - In the opinion of the investigator, the participant should be excluded due to an abnormal physical examination.
 - Current pregnancy
 - Body Mass Index > 35
 - History of migraines (PI discretion)
 - History of drug abuse in the last 6 months
 - History or presence of any clinically significant medical condition, behavioral or psychiatric disorder (including suicidal ideation), or surgical history based on medical record or patient report that could affect the safety of the subject or interfere with study assessments or in the judgment of the PI participant is not a good candidate.
 - Urinary or fecal incontinence
 - Difficulty sleeping in unfamiliar environment (good sleep quality group only)

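### Baseline home sleep efficiency has no stated analytic use beyond the 85% split; pre-specify it as an Aim 2 covariate and in a supportive Aim 1 regression

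*Combined protocol and SAP*

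**What the plan says.** Baseline sleep quality assessment averages two weeks of home actigraphy and calls 85% or more good and anything lower poor. The inclusion criteria repeat the cut-off and add that "this will be determined following enrollment and participants not meeting this criterion will be excluded from further participation in the study".

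Statistical Analysis and Power Calculation compares the groups by repeated measures ANOVA, or by its covariance version when covariates are included. Age is given as an example of a covariate. Average concentration during sleep "will be tested by the main effects of subjects' groups, adjusting for the possible effects of age".

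Assignment to a study group randomises the 45 poor sleepers at admission into three arms of 15. It gives no stratification factor.

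The Background reports preliminary data suggesting that "higher sleep efficiency (total sleep time/time in bed) is associated with a reduction in" Aβ concentration, in both control and drug-treated participants.

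No section makes the measured sleep efficiency a covariate, a continuous predictor or a stratification factor. The second actigraphy period, from the pre-admission visit to discharge, also has no stated analytic use.

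**The concern.** The hypothesised exposure is sleep efficiency, and it is measured on a continuous scale in everyone before assignment. After the split, the plan treats 60% and 84% alike, and 84.9% and 85.1% as opposites. If Aβ falls steadily as sleep efficiency rises, two things are given up.

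- **Aim 1:** the group test does not use the within-group part of the relation, so it cannot describe a gradient and may be less sensitive than it could be.
- **Aim 2:** a baseline variable that the plan itself expects to be related to the outcome is left in the residual variance. With 15 per arm, chance differences in it between arms are common.

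Participants undergo 36 hours of lumbar catheter sampling, and the plan foresees possibly adding more of them after an interim look. Using data already collected is the cheaper source of precision.

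**Working it through.** **1. The plan's own figure.** Inputs from Statistical Analysis and Power Calculation: two-sided two-sample t-test, α=0.05, 80% power, smallest d=1.17, and the claim of detectable differences "between all groups and all A β isoforms with 13 participants in each group". The noncentral t calculation gives n=12.50, hence 13 per group, so the figure reproduces. Power is 81.6% at 13. At the planned 15, the noncentrality is 1.17×√(15/2)=3.20 on 28 df and power is 87.1%. Power stays at 80% down to d=1.06.

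**2. Aim 2 with baseline sleep efficiency as a covariate.** With correlation ρ between covariate and outcome within arms, the residual SD shrinks by √(1−ρ²). The effective size becomes about d/√(1−ρ²), and one degree of freedom is lost (27 instead of 28). For example, ρ=0.4 gives 1.17/√0.84=1.28, and ρ=0.5 gives 1.17/√0.75=1.35. Simulated power for one drug arm against placebo, 15 per arm, d=1.17:

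| ρ (assumed) | Unadjusted | Adjusted |
|---|---|---|
| 0 | 87% | 85-86% |
| 0.2 | 87% | 87-88% |
| 0.3 | 87% | 89% |
| 0.4 | 87% | 91% |
| 0.5 | 87% | 94% |
| 0.6 | 87% | 96% |

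The documents give no value of ρ.

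**3. Chance imbalance in Aim 2.** The standard error of the difference in mean baseline sleep efficiency between two arms is √(2/15)=0.365 SD. The chance that it exceeds 0.5 SD is P(|Z|>0.5/0.365)=17% for one drug arm against placebo, and 29% for at least one of the two. On the outcome scale, a 0.5 SD imbalance at ρ=0.4 moves the contrast by 0.4×0.5=0.2 SD, against a planned effect of 1.17 SD.

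**4. Aim 1, group test against regression on the measured value.** Assumptions: sleep efficiency is normal with mean 80-83 and SD 5-7; 15 people are drawn from each side of 85; the group difference is fixed at d; and a varying share of that difference is a step at 85%, with the rest linear. Power at d=1.17:

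| Share that is a step | Group test | Regression |
|---|---|---|
| 0% (linear) | 87-88% | 97-98% |
| 50% | 87% | 88-89% |
| 75% | 87% | 79-80% |
| 100% | 87% | 66-68% |

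With half-normal, uniform and skewed shapes instead, the linear case gives 87-89% against 96-99%. The full step gives 66% (half-normal) or 58% (skewed) for the regression. At d=0.8, which is my assumption and not a value in the documents, the group test has about 54-57%. The regression then has 74-77% if linear (normal case), 58% at half step and 38-39% at full step.

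**The case against.** The strongest reply is that nothing in the plan is broken. Hypothesis 1 compares two groups, the planned test addresses it, and power exceeds the 80% target at the smallest stated effect. This stands. A reader might infer from the dichotomy that Aim 1 is underpowered; that needs an effect below d=1.06, and the documents give none. The regression advantage also rests on near-linearity. The Background reports an association without giving its shape, and the advantage is almost gone once half the difference is a step.

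Second, the covariate list is open, so sleep efficiency could still enter. This stands in part. It would be too strong to say that the measurement is discarded; the supportable statement is that no use of it is pre-specified. But the Data and Safety Monitoring Plan promises pre-specified comparisons, and an open list does not supply that.

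Third, randomisation keeps the Aim 2 estimate unbiased and its standard error already allows for chance imbalance. This stands: the gain is precision only. The plan also analyses change by repeated measures, which may absorb stable differences between people and leave a smaller ρ than the Background would suggest.

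A reader might go further and argue that many poor sleepers leave the drug little room to act, since the cited trial found that "suvorexant 10 mg increased sleep efficiency from 65.1% at baseline to 82.9% at night 1 and 84.4% at one month" while this trial admits anyone below 85%. The documents do not support that as a finding. The cited figures come from patients with primary insomnia, and how sleep efficiency was measured there is not stated. The protocol itself says that actigraphy reads higher than polysomnography and that its cut-offs were raised for that reason. The comparison is indicative at most.

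**Conclusion.** The point holds as a modest gain in efficiency and information, not as a flaw in validity. Two-week sleep efficiency is available before assignment, is central to the hypothesis, and has no stated role after the 85% split.

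In Aim 2, at d=1.17, adjustment is worth about 4-7 points of power if ρ is 0.4-0.5, nothing at about 0.2, and costs 1-2 points at 0. In Aim 1, the regression gains about 10 points if the relation is linear and loses about 20 if it is a step at 85% (normal distribution assumed; nearer 30 with the skewed shape). It can therefore support the group test but must not replace it. All of these figures rest on assumed correlations and distributions, because the documents give neither.

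The eligibility sentence might be read as removing people near the cut-off, or as a design fault because it removes nobody. It is a clerical slip with no effect on the analysis: the other sections make clear that the value assigns a group.

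**What to change.** In Statistical Analysis and Power Calculation, pre-specify:

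- **Aim 2:** the two-week baseline actigraphy sleep efficiency, as a continuous covariate in the comparison of each suvorexant arm with placebo. Name the screening average explicitly. Actigraphy recorded after dosing must not be used, because treatment can affect it.
- **Aim 1:** the good-versus-poor group test remains primary. Add a regression of Aβ on continuous baseline sleep efficiency in the 30 placebo participants, labelled supportive and placed outside the primary multiplicity correction.

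Stratifying the randomisation of the 45 by baseline sleep efficiency is optional. In the inclusion criteria, reword the sentence so that the measurement assigns a group rather than excludes.

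The cost is a few lines of text, one model degree of freedom and a linearity assumption in each model. No added participants, visits or measurements are needed.

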Baseline sleep quality assessment: Participants meeting the inclusion/exclusion criteria described above will then be assessed for sleep efficiency at home with sleep diaries and actigraphy (Actiwatch2TM; Respiration, Bend, OR) for two weeks. In the case of a subject currently receiving medication that would interfere with the accuracy of sleep efficiency assessment in the opinion of the investigator, the participant will be asked to washout of the medication prior to baseline actigraphy collection. The minimum discontinuation period for washout is generally 9 half-lives of the medication, but will be determined by the investigator.

Sleep diaries and actigraphy are well-established methods for assessing sleep at home, and are methods we have used previously. Participants an average sleep efficiency of $\geq 85\%$ over the two week period will be considered to have “good” sleep quality; participants with an average sleep efficiency $< 85\%$ will be determined to have “poor” sleep quality. We have set our sleep efficiency cut offs for poor and good sleep quality higher than used in our preliminary data because of the differences in measuring sleep efficiency by actigraphy compared to PSG.

Actigraphy over-estimates sleep efficiency compared to PSG (45), therefore higher cutoffs will be used when screening with actigraphy.

Sleep quality assessment prior to admission: Participants meeting enrollment criteria will be scheduled for an office visit 7 ± 3 days prior to admission at the Clinical Research Unit. Participants will be dispensed a sleep diary and an actiwatch. They will be asked to continue the sleep diary and actigraphy collection until the day of discharge at the Clinical Research Unit.

Aim 1: To determine the effect of poor sleep efficiency on CNS A β kinetics.

15 participants with sleep efficiency $\geq 85\%$ and 15 participants with sleep efficiency $< 85\%$ measured by actigraphy will be admitted to the CRU at Washington University in the afternoon

(Day 1)). All participants will have their sleep monitored with PSG (ex. TrackItTM; Lifelines, Troy, IL) that will allow for sleep staging according to the gold standard American Academy of Sleep Medicine criteria (46). Participants will be monitored with PSG throughout the CRU admission.

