Intravenous Catheter

1. Discomfort from minor pain, bleeding, bruising, or swelling caused by the needle or intravenous catheter are common and mild.
2. Bruising at the phlebotomy site is infrequent and mild. Some individuals may have bruising due to leakage of a small amount of blood from the vein into the surrounding tissue. This will spontaneously resolve.
3. Feeling faint is common and mild. As with any medical procedure, some people feel faint. This is a normal response and is *not* a physical effect of the needle.

Suvorexant

1. Somnolence and confusion are common, mild side effects of suvorexant in participants who wake up within 4-6 hours after taking the drug. This is an expected effect of this drug given its mechanism of action. However, somnolence may be severe in participants with compromised respiratory function; therefore obstructive sleep apnea and chronic obstructive pulmonary disease are exclusion criteria.
2. Next day drowsiness is another common, mild side effect of suvorexant. Participants will be monitored in the Clinical Research Unit prior to discharge and will be assessed for level of alertness with a Stanford Sleepiness Scale and psychomotor vigilance testing performed upon admission and at the time of discharge. The principal investigator will evaluate the participant and review these measures prior to approving discharge.
3. Additional mild and common reactions to suvorexant include: headache, dizziness, abnormal dreams, diarrhea, dry mouth, and cough.
4. Abnormal sleep behaviors, such as sleep walking, is rare and mild-to-moderate. All participants will take suvorexant on the Clinical Research Unit at Washington University that has 24 hours a day nursing coverage monitoring the participants.
5. Suvorexant may interact with multiple medications including alcohol, azole antifungals, antibiotics, nefazodone, antiretrovirals, conivaptan, aprepitant, diltiazem, imatinib, verapamil, rifampin, carbamazepine, phenytoin, and digoxin. The principal investigator will evaluate participants for potentially interacting medications and participants will be excluded from the study if the interacting drug(s) cannot be discontinued.

6. Very rare: For all individuals, but primarily in depressed participants treated with sedative-hypnotics, worsening of depression and suicidal tendencies have been reported.

Actigraphy

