1. Somnolence and confusion: Participants will be on the Clinical Research Unit throughout the study with 24-hour nursing coverage. Participants will only take suvorexant in this monitored setting. Nurses will be available to assist all participants if they wake up confused and somnolent during the night. Further, the participants will be under constant video

monitoring while in the Clinical Research Unit; this video is not recorded and is only viewable by the nursing staff. Somnolence may be severe in participants with compromised respiratory function; therefore, obstructive sleep apnea and chronic obstructive pulmonary disease are exclusion criteria. Suvorexant will be discontinued if somnolence and/or confusion is distressing to the participant or severe.

2. Next day drowsiness: Participants will be monitored in the Clinical Research Unit prior to discharge and will be assessed for level of alertness with a Stanford Sleepiness Scale and psychomotor vigilance testing performed upon admission and at the time of discharge. The principal investigator will evaluate the participant and review these measures prior to approving discharge.
3. Additional mild and common reactions to suvorexant include headache, dizziness, abnormal dreams, diarrhea, dry mouth, and cough: Participants will be on the Clinical Research Unit throughout the study with 24-hour nursing coverage. Participants will only take suvorexant in this monitored setting. Nurses will be available to assist all participants if they develop these symptoms. Suvorexant will be discontinued if reactions are distressing to the participant or severe.
4. Abnormal sleep behaviors: All participants will take suvorexant on the Clinical Research Unit at Washington University which has 24 hours a day nursing coverage monitoring the participants. Participants will only take suvorexant in this monitored setting. Nurses will be available to assist all participants if they develop these symptoms. Further, the participants will be under constant video monitoring while in the Clinical Research Unit; this video is not recorded and is only viewable by the nursing staff. Suvorexant will be discontinued if reactions are distressing to the participant or severe.

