5. Suvorexant may interact with multiple medications: Participants taking medications that interact with suvorexant will be evaluated by the principal investigator. If the potentially interacting medications cannot be discontinued, then the participants will be excluded from the study.
6. Depressed mood and/or suicidal ideations: All participants will be screened for suicidal ideations and psychiatric disorders. All participants with psychiatric disease requiring medications will be excluded both to control this risk and also because psychiatric medications may interfere with sleep. Participants with suicidal ideations will be excluded. This risk is also controlled because participants will only take suvorexant for 2 nights in the monitored setting of the CRU with 24 hours a day nursing coverage.

Actigraphy

1. Irritation of skin from strap of actigraph: Participants will be permitted to wear the actigraph over long sleeves or a wrist band, or they can remove the actigraph at any time.

Polysomnogram (Sleep study)

1. Irritation of skin from electrodes used during study: When possible, an alternative cleaning agent or adhesive will be used. If irritation is more than mild, that electrode will not be used for the study.
2. Worse sleep quality: Participants will be allowed to nap until 17:00 before going home after the conclusion of the study.

Privacy/confidentiality

1. Breach of privacy/confidentiality:
 - All data will be labeled with a random number rather than with any identifiable information. All physical materials (such as paper, data storage disks, and biospecimens) will be stored in locked cabinets/freezers in a locked research area, accessible only to the research team. All electronic information will require a password and will be accessible

- only to the research team. Any paper or electronic information that could link a participant to the study (such as consent documents) will be stored separately from all other study materials, also in a secure manner that is accessible only to the research team. If a report or article is written about this study or the study data are shared with other researchers, it will be done in such a way that participants cannot be identified.
- For individuals who give verbal consent for the Phone screen, and then do not “pass” the screening questions, their phone screen will be shredded, and *no* information is kept about them.

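### The exclusion list leaves medicated psychiatric disorder and COPD to the investigator's discretion, while the suvorexant safety text excludes both outright

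*Combined protocol and SAP*

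**What the plan says.** The exclusion criteria in section 1.A mark several items as subject to the investigator's discretion. Two matter here: "Neurologic or psychiatric disorder requiring medication (PI discretion") and "Pulmonary disease (PI discretion"). COPD is not named anywhere in that list.

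The suvorexant safety text treats both conditions as settled:

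- **Psychiatric disease.** Section 2.B (Protections Against Risk), Suvorexant item 6: "All participants with psychiatric disease requiring medications will be excluded both to control this risk and also because psychiatric medications may interfere with sleep". The risk referred to is depressed mood or suicidal ideation.
- **COPD.** Section 1.C (Potential risks), Suvorexant item 1, says somnolence may be severe when respiratory function is compromised, "therefore obstructive sleep apnea and chronic obstructive pulmonary disease are exclusion criteria". Section 2.B, Suvorexant item 1, repeats it: "Somnolence may be severe in participants with compromised respiratory function; therefore, obstructive sleep apnea and chronic obstructive pulmonary disease are exclusion criteria".

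The adverse-event plan in section 2.B then cites the inclusion and exclusion criteria as one of the means by which suvorexant risk is minimised.

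**The concern.** The protocol gives two different rules for the same people. Someone with mild COPD, or with a stable psychiatric disorder controlled by medication, can be admitted under the list and is barred by the safety text. The safety argument relies on the criteria, and for these two conditions the list does not contain the safeguard described.

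The psychiatric case has a further consequence. A participant admitted under discretion could go one of two ways:

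- They stay on a drug that section 2.B says may interfere with sleep, which is the exposure under study.
- If the investigator judges that the drug would distort the sleep-efficiency assessment, "the participant will be asked to washout of the medication prior to baseline actigraphy collection" (Baseline sleep quality assessment). A poor sleeper in that position could stop the drug and then be randomised to suvorexant.

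Section 1.C, Suvorexant item 6, describes the hazard, which it labels very rare: "primarily in depressed participants treated with sedative-hypnotics, worsening of depression and suicidal tendencies have been reported". The strict rule in section 2.B avoids both routes because that person would never have been enrolled.

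**Working it through.** The plan gives no figure to reproduce on this point. The check sets the texts side by side and then counts how far the conflict reaches.

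**Step 1: compare the rules.** The suvorexant safety text names four medical conditions as excluded.

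| Condition | Suvorexant safety text (1.C, 2.B) | Exclusion list (1.A) | Agree? |
|---|---|---|---|
| Obstructive sleep apnea | Excluded | Sleep disorders other than insomnia, no discretion | Yes |
| Suicidal ideation | Excluded | Listed, no discretion | Yes |
| Psychiatric disease requiring medication | All excluded | Discretionary | No |
| COPD | Excluded | Not named; falls under discretionary pulmonary disease | No |

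Two of the four are unconditional in the list and two are not.

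**Step 2: count the discretionary items.** They are cardiovascular disease requiring medication, pulmonary disease, neurologic or psychiatric disorder requiring medication, alcohol or tobacco use, sedating medications, and migraines. That makes six, of which two conflict with the safety text.

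**Step 3: see whether another criterion closes the gap.**

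- The catch-all begins "History or presence of any clinically significant medical condition, behavioral or psychiatric disorder (including suicidal ideation), or surgical history" and goes on to require that the condition could affect safety or interfere with assessments, or that the investigator thinks the person a poor candidate. That is a judgment. It narrows the gap to mild COPD and stable medicated psychiatric disorder but guarantees neither exclusion.
- The sedating-medications item is itself discretionary.
- The intention to enrol healthy adults (1.A, Subject population characteristics) is worded as a goal.

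**Step 4: reach.** Arm sizes come from 1.A, Assignment to a study group.

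- Can be randomised to suvorexant: 45/60 = 75%.
- Receive it: 15 + 15 = 30, and 30/60 = 50%, with two doses each.
- Placebo only by design (good sleepers): 15/60 = 25%.

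The respiratory reason for excluding COPD does not reach the good sleepers. The sleep-interference reason for excluding psychiatric medication applies to all 60. These are counts of people to whom the rules apply, not estimates of risk.

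**Step 5: would monitoring catch it in time?** The safety committee monitors adherence to the protocol and the eligibility criteria (section 5), so it could call such an enrolment a deviation. Its scheduled meetings follow 15, 23, 30, 38 and 45 completions (2.B, Reporting Procedures). An affected participant would usually have been dosed before the next review.

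**The case against.** The strongest reply is that the document can be read as a whole. Pulmonary disease is a broad class, so it can be discretionary in general while COPD is excluded by the safety text. On that reading COPD merely lacks its own line. This has some force, and the COPD conflict is the weaker of the two. It still leaves sections 1.C and 2.B asserting a criterion that the list does not contain. The psychiatric conflict cannot be read away, because the same condition is discretionary in one place and excluded for everyone in the other.

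Second, the Participants paragraph refers to a Table 2 of all criteria, which is not in the text available for this review. It may state both exclusions outright, so it is uncertain that screening would follow the discretionary wording. Section 2.B also requires screening for psychiatric disorders. This limits what can be said about practice. It does not remove the conflict between the section 1.A list and the safety text.

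Third, the practical risk is small. Suicidal ideation is excluded absolutely, the catch-all removes clinically significant cases, and the investigator reviews interacting drugs. There is one site. Dosing is two inpatient nights with 24-hour nursing, video monitoring and discontinuation for severe reactions. The washout provision names no psychiatric drug, so that route is conditional. All of this stands and keeps the severity at low to moderate.

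Last, the COPD statements sit under a suvorexant heading and concern drug-induced somnolence, so applying them to placebo-only good sleepers goes beyond their stated reason. That is fair. The case for one common rule rests on comparability in Aim 1.

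**Conclusion.** The concern holds, and the wording should be fixed. As written, the section 1.A list could admit people whom the protocol's own safety text bars. The contradiction is direct for psychiatric disorder requiring medication. For COPD, a stated criterion is absent from the list. Confidence in this textual finding is high.

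The remaining gap is mild COPD or stable medicated psychiatric disorder accepted under the discretionary items. How many such people would be enrolled cannot be estimated from the documents. No effect on power or on the planned analysis is claimed. The conclusion covers the section 1.A list and the suvorexant items in 1.C and 2.B. It assumes nothing about the content of Table 2.

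**What to change.** In the section 1.A exclusion criteria, and in Table 2 if it differs:

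- List chronic obstructive pulmonary disease as an exclusion without discretion.
- List psychiatric disorder requiring medication as an exclusion without discretion.
- Keep discretion for other pulmonary disease and for neurologic disorder requiring medication.

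Apply both exclusions to all 60 participants. The safety text limits neither to a treatment group, and a common rule holds the good-sleep group to the same medical criteria as the poor-sleep placebo group it is compared with in Aim 1.

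The cost is a short wording amendment and some additional screen failures, probably few, though the documents do not allow a number. Recruitment draws on a registry of more than 10,000 volunteers. The investigator loses the freedom to admit mild COPD or stable medicated psychiatric disorder, which the safety text already disclaims. Softening the safety text would also remove the conflict, but only by withdrawing a stated safeguard.
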